Divergent findings regarding differences in SUI scores between those classified as underreporting and those producing scores within normal limits on content-based validity scale scores support the further clinical need for examining the impact of MMPI-indexed underreporting on suicide-related criterion, including those embedded into the MMPI. While no significant mean differences in MMPI-2-RF SUI scores between these two groups have been observed (Crighton et al., 2017), including in Veteran samples (Forbey et al., 2013; Khazem et al., In Press), significant differences with small-sized effects have also been observed in other samples (Brown & Sellbom, 2020; Khazem et al., In Preparation). Further, as these studies were not aimed at identifying patterns of responding for individuals attempting to conceal suicidal ideation or intent, it is unclear how these individuals, particularly within the Veteran population, would respond to SUI items - and extratest measures of suicide risk and psychopathology. Research employing a simulated groups design in Veteran-serving clinics unaffiliated with VA is well-suited to address these limitations and expand upon previous findings.

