Participants could develop mild to moderate emotional discomfort or frustration associated with completing questionnaires or answering interview questions assessing thoughts about suicide. This potential risk is expected to be comparable to the discomfort experienced when talking with a friend or acquaintance about these same topics. If discomfort is experienced, it is not expected to be severe or to last for more than a few minutes. Participants' *confidentiality could be breached* if their identifiers are inadvertently released or accessed by a third party. This risk is expected to be low because the data are not stored or analyzed in ways that are likely to reveal a subject's identity. Breach of confidentiality could also occur if an external party or individual hacks into the Zoom interface during a participant's session. Safeguards will be implemented to mitigate this risk, including using password-protected Zoom sessions.

2.3. Benefits of the Proposed Research Results of this proposed research will have implications for future suicide risk assessment and suicide prevention efforts in Veterans through enhancing methods of identifying and responding to those at risk of suicide that would otherwise be missed by traditional methods of suicide risk assessment (i.e. false negatives).

Procedures

3.1. Research Design. A two-arm randomized controlled simulation design will be employed in this proposed research. For both components of the study, participants will be randomized using stratified blocks of 6 or 8 participants, per recommendations by Krenan et al. (1999), based on gender and suicide attempt history (no history of suicide attempts, history of one suicide attempt, or history of multiple suicide attempts).

3.2. Sample. A sample of 150 Veterans will be included in the study and randomized to study conditions (75 in the Simulation condition and 75 in the Standard condition). Results of a priori power analyses conducted using G*Power software (Faul et al., 2007) indicate that a total sample of 150 will result in a highly-powered study ($\beta = .98\text{--}.99$) to detect medium-sized effects in all regression-based analyses. Therefore, although we anticipate low attrition from this study, the proposed sample size is sufficiently powered for the proposed analyses. Additionally, this sample size accounts for a roughly 15% rate of Non-Content-Based Invalid Responding observed in other simulation-based MMPI research (Crighton et al., 2017).

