3.4. Informed Consent and Confirmation of Eligibility

Informed consent will be obtained through Qualtrics survey software from each participant prior to initiation of study tasks. Study personnel will obtain informed consent from participants and answer questions about the study or informed consent process prior to beginning study activities. Following informed consent, participants will complete a demographics questionnaire through Qualtrics that also includes items assessing history of suicide attempts from the Self-Injurious Thoughts and behaviors Interview (Nock, Holmberg, Photos, & Michel, 2007) for study eligibility determination and randomization purposes as well as the Suicide Visual Analog Scale (Bryan, 2019). Regardless of eligibility, all participants will be provided with contact information for crisis resources including the National Suicide Prevention Lifeline and Veterans Crisis Line.

3.5. Randomization to Study Conditions.

REDCap, a secure online survey and data management system maintained by The Ohio State University, will be utilized to randomize participants to study conditions immediately after obtaining demographic information (man, woman, other) and information about suicide attempt history (no suicide attempts, one suicide attempt, more than one suicide attempt) obtained from the SITBI). Participants will be randomized using stratified blocks of 6 or 8 participants, per recommendations by Krenan et al. (1999). After randomization, each participant will complete the remainder of the research study, but will be presented with one of the following pages containing instructions for completing the MMPI-2-RF-EX.

MMPI Condition 1 (Standard Instructions): “We want you to imagine that you are undergoing psychological testing as part of standard intake procedures for receiving services in a mental health clinic, which involves completing some questionnaires and a personality test before the first session. Please answer the questionnaires as honestly as you can, as your mental health care provider will use the results of your testing to develop your treatment plan. Please note, the questionnaire has some “lie” scales built into it that detect false responding. Additionally, as part of the intake process, you agreed to identify questions that you think are assessing your current risk of suicide. You will open the link to this portion of the study that was sent to you by study personnel to complete this.”

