consenting, demographics survey and self-reported history of suicide attempts, randomization to study conditions, the MMPI-2-RF-EX, self-report measures, and the post-test survey to assess compliance with study instructions. Consenting procedures will always be completed first, and demographic and suicide attempt history data will always be collected second for randomization to conditions in both components of the study through REDCap online software. We estimate that the total participation time will be approximately 2.5 hours (2 hours to complete the MMPI-2-RF-EX and extra-test self-report measures. In order to protect participant confidentiality, password-protected Zoom or phone-based sessions will be conducted during the baseline session, in order to ensure security of MMPI-2-RF-EX items. All data will be collected through the Qualtrics, and non-PHI demographic information will be entered into REDCap system for randomization purposes. ID numbers will be linked to all data collected in the study, including identifying information collected in a separate data set as part of safety procedures (See Section 3.7), which will be deleted at the conclusion of the study. All deidentified data will be downloaded and deleted from Qualtrics servers at the conclusion of the study and stored on the password protected OneDrive server hosted by OSU indefinitely for the proposed analyses and secondary analysis. Additionally, in order to protect participant privacy during the study, all study personnel will conduct study procedures from a private location, using a secure Internet connection and instruct all participants to do the same, if possible, and outline the risks of loss of privacy or confidentiality if the participant is unable to do so.

3.7. Internal Validity. A number of measures will be implemented to mitigate threats to internal and external validity. Specifically, the randomization procedures employed in the proposed research study (See Section 4.1.2) were selected to account for the potential influences of gender and suicide attempt status on study findings.

3.8 Data Analysis.

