3.8.1. MMPI-2-RF-EX scale scores and extra test measures. Following methods employed in prior simulation research designs (Sellbom & Bagby, 2008), mean differences in scores on MMPI-2-RF-EX L, K, and SUI scales, and extratest measures of suicide risk (BSS), suicide-related cognition intensity (SCS), and measures of other psychopathology (PCL-5, Short Grit Scale) will be compared between Standard and Simulated Underreporting groups through a one-way Multivariate Analysis of Variance (MANOVA). Additionally, two stepwise hierarchical regression analyses will be conducted in order to assess the incremental predictive utility of MMPI-2-RF-EX K and L scales in identifying individuals classified in the Simulated Underreporting condition, consistent with previous literature (Sellbom & Bagby, 2008). The first model will contain the K scale in the first step and the L scale in the second step. The analysis will be repeated with the K and L scales entered into the opposite step.

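### The group comparison ignores the randomisation strata and the Suicide Visual Analog Scale; adjusting would change precision on SUI, SCS and BSS by anything from a negligible loss to a moderate gain

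*Combined protocol and SAP*

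**What the plan says.** Section 3.8.1 states that L, K, SUI, BSS, SCS, PCL-5 and Short Grit scores "will be compared between Standard and Simulated Underreporting groups through a one-way Multivariate Analysis of Variance (MANOVA"), following earlier simulation studies. It names no covariate and no stratum term.

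The design already uses two baseline factors. Section 3.5 says "Participants will be randomized using stratified blocks of 6 or 8 participants", and section 3.1 gives the strata as gender and suicide attempt history (none, one, multiple). Both are known before allocation: REDCap will "randomize participants to study conditions immediately after obtaining demographic information" and attempt history, and Detailed Study Procedures says "demographic and suicide attempt history data will always be collected second for randomization to conditions". Internal Validity (section 3.7) explains that the randomisation procedures "were selected to account for the potential influences of gender and suicide attempt status on study findings".

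The VAS appears once. Informed Consent and Confirmation of Eligibility places it with the post-consent demographics questionnaire, whose attempt-history items serve "for study eligibility determination and randomization purposes as well as the Suicide Visual Analog Scale". No analysis mentions it.

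**The concern.** When allocation is balanced within strata that predict the outcome, an analysis without those strata leaves between-stratum variance in its error term. The estimate stays unbiased, but the standard error is too large and the test is conservative. A baseline measure of suicide risk that predicts the outcome would also remove residual variance.

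What is at stake is precision for H2 (SUI, SCS, BSS). Nothing in the documents links these covariates to L or K, so no gain is claimed there. Nor do the documents give an expected effect for this contrast. Section 2.1.2 says of earlier SUI findings, which were null or small, that "these studies were not aimed at identifying patterns of responding for individuals attempting to conceal suicidal ideation or intent". A modest difference therefore cannot be ruled out, and modest differences are where precision matters.

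**Working it through.** **1. The plan's own power figure.** Section 3.2 gives .98–.99 (printed as β, evidently meaning power) for medium effects in regression-based analyses with N = 150. Effect size and alpha are not stated. Assuming f² = 0.15 and alpha 0.05, the noncentrality is λ = f²N = 0.15 × 150 = 22.5. Power is 0.992 with two predictors, 0.985 with three, and 0.997 for the R² increase from one of two predictors. The figure is reproduced, but it describes the regressions and not the group comparison.

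**2. Analysable sample.** Section 3.2 says "this sample size accounts for a roughly 15% rate of Non-Content-Based Invalid Responding". 150 × 0.85 = 127.5, or about 64 per arm.

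**3. Unadjusted comparison of one scale.** A two-sided 0.05 t test has power 0.39, 0.80 and 0.99 at d = 0.3, 0.5 and 0.8. No d is taken as expected. The 95% half-width is 1.979 × √(4/127.5) = 0.350 SD at any d.

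**4. Adjusted comparison, closed form.** With k covariate degrees of freedom, the variance ratio is (1 − R²)(N − 3)/(N − k − 3). Here k = 5 (gender 2, attempts 2, VAS 1) and N = 127.5, so the second factor is 124.5/119.5 = 1.042. At d = 0.5:

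- R² 0: ratio 1.042; power 0.800 to 0.783.
- R² 0.10: ratio 0.938; power 0.800 to 0.824.
- R² 0.20: ratio 0.833; power 0.800 to 0.866.

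Break-even is R² of about 0.04. This formula charges for chance covariate imbalance, which stratified blocks largely prevent, so it understates the gain somewhat.

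**5. Monte Carlo check under the design.** Settings: N = 150, stratified blocks of 6 or 8, 15% random exclusions, HC2 standard errors, 20,000 trials. Assumed: gender shares 80/18/2, attempt shares 55/25/20, total R² split equally between strata and VAS, equal slopes in both arms. Each cell is unadjusted to adjusted.

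| Total R² | Power, d = 0.3 | Power, d = 0.5 | Half-width (SD) | Null size |
|---|---|---|---|---|
| 0 | .394 to .385 | .801 to .796 | .350 to .353 | .050 to .050 |
| 0.10 | .391 to .423 | .804 to .833 | .350 to .335 | .047 to .050 |
| 0.20 | .390 to .464 | .804 to .876 | .350 to .316 | .043 to .052 |

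At d = 0.8, unadjusted power is already .993 or more. If R² 0.20 comes wholly from the strata, null size is .035 unadjusted and .050 adjusted. In participants, (.3503/.3347)² × 127.5 = 140, about 12 more; (.3504/.3157)² × 127.5 = 157, about 30 more.

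**6. Unequal slopes.** Condition 2 tells participants to conceal suicidality, so covariates may predict less in that arm.

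- Half the slope, Standard-arm R² 0.20: .384 to .418 at d = 0.3; .800 to .833 at d = 0.5.
- No slope, Standard-arm R² 0.10: .394 to .392 and .804 to .804; half-width .350 to .348.
- No slope, Standard-arm R² 0.20: .393 to .402 and .803 to .809; half-width .350 to .344.

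A smaller run (1,500 trials, N = 150, no exclusions, d = 0.5) with no slope in the simulated arm gave .863 to .859 when the Standard-arm correlation was 0.3 and .856 to .879 when it was 0.5. Across these runs the change is about 0 to 2 points.

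**7. Omnibus test.** Seven scales, residual correlation .5, effect on five scales, covariates related to SUI, SCS and BSS only, d = 0.3, 6,000 trials:

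- R² 0: .622 to .613.
- Equal slopes: .583 to .646 (R² 0.10); .555 to .684 (R² 0.20).
- No simulated-arm slope: .597 to .607 (R² 0.10); .587 to .610 (R² 0.20).

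Gains of 6 to 13 points shrink to 1 to 2; half slopes give 3 to 7. At d = 0.5 with equal slopes, all values are at least .98. These figures depend on the assumed correlations.

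**The case against.** The strongest reply is that nothing is broken. The MANOVA is valid, it was chosen for comparability with earlier simulation studies, and the plan nowhere promises adjustment. A reader might infer from Internal Validity that the analysis contradicts a commitment to account for gender and attempt status. It does not: that section credits the randomisation procedures, and sections 3.1 and 3.5 deliver them. Nor do the documents support a reading that the unadjusted test is biased or anti-conservative.

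A reader might also take the R² 0.20, equal-slope row as the likely gain. The documents do not support that either. They give no correlation, and the concealment instruction makes equal slopes the least plausible case. Eligibility requires past-month ideation or attempt, which may narrow the VAS range. Incentives are described at consent, before the VAS; this is the same in both arms but could weaken the VAS as a measure of risk.

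Finally, a reader might treat the VAS as certainly pre-randomisation. That is only inferred from its place in the consent section. The component list in Detailed Study Procedures does not mention it, and section 3.5 triggers randomisation after demographics and attempt history. Only the strata are certain.

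All of this stands and limits the size of the point. It does not remove it: the strata are known before allocation, and the downside of using them is small.

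**Conclusion.** The point holds as a missed efficiency that the plan should take up; the validity of the planned test does not depend on it. At about 64 per arm and d = 0.5, the change in single-scale power runs from a loss (under 1 point by Monte Carlo, up to about 2 by closed form, if the covariates predict nothing), through 0 to 2 points if simulators' answers do not track true risk, to about 3 points at R² 0.10 and 7 to 8 at R² 0.20 with equal slopes. At d = 0.8 there is nothing to recover.

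Every R², slope and stratum share is an assumption, and the larger figures also need the VAS to be a true baseline. Adjustment does not repair the condition-specific exclusions after randomisation described under Posttest Inquiry, which can bias either analysis. Confidence is medium.

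**What to change.** In section 3.8.1:

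- Pre-specify gender and attempt history as main effects in the group comparison (a MANCOVA), not as nine stratum cells, with a rule for collapsing a sparse 'other' gender category.
- Follow with per-scale ANCOVAs for SUI, SCS and BSS using HC2 standard errors, since slopes and variances may differ by arm. HC2 protects these models only; the MANCOVA still assumes common slopes.
- Add the VAS as a covariate only if the plan confirms that it is completed before randomisation and before the instruction page.
- Keep the unadjusted one-way MANOVA as a sensitivity analysis, for comparability with earlier studies.
- Treat any model with centred condition-by-covariate terms as sensitivity only. With no simulated-arm slope and Standard-arm R² 0.20, it raised power to .427 at d = 0.3 and .827 at d = 0.5, but its null size was about .056.

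The cost is SAP wording and a few lines of code, with no new data. With the VAS, the main model uses four to five degrees of freedom out of about 126, and one fewer without it; the interaction model uses about four more. If the covariates are not predictive, the interval is slightly wider (half-width .350 to .353 SD).

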Online recruitment methods for the study are include web-based survey and research recruitment systems (e.g., SurveyMonkey), listservs and forums, and social media sites (e.g., Facebook, Twitter, Reddit). Additionally, we are requesting use of ResearchMatch (RM), which is an NIH sponsored national registry for research volunteers. ResearchMatch (RM) and OSU have had a fully executed agreement since August 2009. The IRB of record for ResearchMatch is Vanderbilt University. The Principal Investigator will be authorized to recruit study participants.

We will enroll any prospective Veteran meeting inclusion criteria (18 years of age or older, US military veteran, death or suicidal ideation/suicide attempt within the past month) in the proposed study. Exclusion criteria include: non-Veteran status, acute intoxication or active psychosis precluding

provision of informed consent, an inability to communicate and comprehend English, residence outside the United States, and lack of past-month death/suicide ideation or attempt. Participants recruited through web-based survey and research and recruitment systems will provide consent for study personnel to initiate contact through email or phone call, while those recruited through other online methods (e.g., listservs, forums) will be provided contact information for study personnel in order to inquire about the study or schedule participation.

3.3 Measurement/Instrumentation. The following self-report measures will be administered through Qualtrics online survey software during baseline procedures as part of the proposed research:

MMPI-2-RF-EX. The MMPI-2-RF-EX The MMPI-2-RF-EX was developed for research purposes in order to develop the MMPI-3 (Ben-Porath & Tellegen, 2020), which is comprised of a subset of MMPI-2-RF-EX items. While completing the MMPI-2-RF-EX, all participants will be monitored remotely by study personnel using a web camera and OSU CarmenZoom to ensure test integrity, as required by the study funding agency. While completing the MMPI-2-RF-EX, participants will simultaneously select the MMPI-2-RF-EX item numbers corresponding to those they believe are assessing current suicide risk through a separate internet browser or tab opened to a link in Qualtrics provided by study personnel.

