3.9. Safety Procedures. During enrollment in the study, all participants, regardless of agreement to participate in both portions of the study, will provide their contact information (home address, telephone number, email address) and a telephone number for an alternate person that study personnel may contact in case of imminent suicide risk. Home addresses may be used to contact the participant's local emergency services in case of imminent suicide risk. If a subject reports suicidal ideation, or a research staff member becomes aware that the subject is at imminent risk to harm himself/herself, the following questions will be asked to clarify the nature of risk (and to identify those at imminent risk requiring consideration for hospitalization): (1) Do you have a plan for killing yourself and do you intend to act on the plan?; (2) Do you have a desire to kill yourself that you believe you might act on?; (3) Have you already taken steps to act on your plan? If so, what steps have you taken? Both iterations of the CRP, which is a recommended and empirically-supported strategy for reducing suicide risk, will include contact information for professional resources and crisis services, the National Suicide Prevention Lifeline phone number, and other local behavioral health clinics and emergency departments. These procedures have been used successfully by our research team in dozens of studies with acutely suicidal individuals, to include multiple clinical trials. All participants will be provided with contact information to use in case of crisis (National Suicide Prevention Lifeline, emergency services).

3. Bibliography

Anestis, M. D., & Green, B. A. (2015). The impact of varying levels of confidentiality on disclosure of suicidal thoughts in a sample of United States National Guard personnel. *Journal of Clinical Psychology*, 71, 1023-1030.

Beck, A. T., & Steer, R. A. (1991). *Manual for the Beck scale for suicide ideation*. San Antonio, TX: Psychological Corporation.

Beck, A. T., Ward, C. H., Mendelson, M., Mock, J., & Erbaugh, J. (1961). An inventory for measuring depression. *Archives of General Psychiatry*, 12, 57-62.

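### Section 3.9 names only the home address for reaching local emergency services, although sessions are remote and no step in the supplied text records where the participant is.

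*Combined protocol and SAP*

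**What the plan says.** Section 3.9 (Safety Procedures) says that participants "will provide their contact information (home address, telephone number, email address) and a telephone number for an alternate person", whom staff may contact if suicide risk is imminent. On reaching emergency services it says: "Home addresses may be used to contact the participant's local emergency services in case of imminent suicide risk". If a participant reports suicidal ideation, or staff become aware of imminent risk, "the following questions will be asked to clarify the nature of risk". The three questions cover a plan with intent to act on it, a desire that might be acted on, and steps already taken.

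The section on detailed study procedures (the second section numbered 3.4) says that "password-protected Zoom or phone-based sessions will be conducted during the baseline session". Study personnel are to work "from a private location, using a secure Internet connection and instruct all participants to do the same, if possible". On order, "Consenting procedures will always be completed first, and demographic and suicide attempt history data will always be collected second". The same section mentions "identifying information collected in a separate data set as part of safety procedures (See Section 3.7), which will be deleted" when the study ends. The Section 3.7 it points to is Internal Validity; the safety text is in Section 3.9.

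Section 3.3 adds that, during the MMPI-2-RF-EX, "all participants will be monitored remotely by study personnel using a web camera and OSU CarmenZoom to ensure test integrity". Section 3.2 requires thoughts of death or suicide, or an attempt, within the past month, and excludes people who live outside the United States.

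**The concern.** A home address leads to the right emergency service only if the participant is at home. Nothing in the supplied text ensures this: the session is remote, a private place is asked for only where possible, and the eligibility rule concerns residence and not where the session takes place. Participants may live anywhere in the country, so staff cannot rely on knowing the area.

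This is a question of participant safety. Everyone enrolled has recent thoughts of death or suicide, or a recent attempt, and the three risk questions exist to pick out people who may need hospital care. Section 2.1.1 of the protocol notes that people being assessed for suicide risk may play down distress to stay out of hospital. It does not say that they hide where they are, but it is reasonable to expect some to stop cooperating once hospital care is in view. That is also the moment at which staff would first need the location. Following Section 3.9 as written could then send help to an empty house and lose time.

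**Working it through.** The plan states no figure on this point, so the check is a reading of Sections 3.2 to 3.9 for any step that asks for, confirms or records where the participant is, followed by simple arithmetic on cost.

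**Does any item give the current location?**

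| Source | Content | Current location? |
|---|---|---|
| 3.9, contact items (4) | Home address, telephone, email, alternate person's telephone | 0 of 4 |
| 3.9, risk questions (3) | Plan and intent, desire, steps taken | 0 of 3 |
| 3.4, consent and eligibility | Consent, demographics, attempt history, Suicide Visual Analog Scale, crisis contacts given to participants | No step stated; demographics items not listed in full |
| 3.5, randomization | Gender and attempt history | No |
| 3.4, detailed procedures | Order of steps, session mode, privacy instruction | No |
| 3.7, cited for safety procedures | Internal validity | No |

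The two counts describe what the text contains. They do not measure harm.

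**What do the existing safeguards supply once contact is lost?**

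- Telephone and email work only if the participant answers and is willing to say where they are.
- The alternate person helps only if reachable and aware of the location.
- The web camera is described only for the MMPI-2-RF-EX, to protect test integrity, and a view of a room is not an address.
- The crisis contacts are for the participant to use; they do not tell staff where the participant is.

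The unprotected case therefore needs three things together: imminent risk, being away from home, and a lost connection or a refusal to give the location. The documents give no rate for any of them, so no expected number of cases is offered.

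**What would a location check cost?** Inputs: 150 participants (Section 3.2); a session of about 2.5 hours = 150 minutes (detailed study procedures); 0.5, 1 or 2 minutes per session (assumed). Staff hours = 150 × minutes ÷ 60. Share of session = minutes ÷ 150.

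| Minutes per session (assumed) | Staff time, 150 sessions | Share of session |
|---|---|---|
| 0.5 | 75 min = 1.25 h | 0.33% |
| 1 | 150 min = 2.5 h | 0.67% |
| 2 | 300 min = 5 h | 1.33% |

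**Does it disturb the design?** Contact details are taken at enrollment. A location item at the end of the consenting step comes before demographics, attempt history and randomization, so the stated order is kept and both arms are asked alike.

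**The case against.** The strongest reply is that silence in this text is weak evidence. The consent pages were not available, the demographics items are not listed in full, and Section 3.9 is a summary that also leaves out who places a call and what follows a positive answer. The protocol says that the procedures have worked in dozens of studies with acutely suicidal people. This limit stands, and it is why the point is confined to the supplied text. The statement about past studies, however, does not say that they were remote or that they recorded location.

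Second, the wording on home addresses is permissive, and staff have a telephone number, an email address, an alternate contact and a live conversation in which to ask. All true, and these safeguards cover most situations. They do not supply a location once the participant has gone and nobody who can be reached knows it.

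Third, the remaining case is narrow and probably rare. That is accepted.

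Fourth, the remedy is imperfect. Participants may decline or misstate where they are, and suicide is already the subject of the study when they are asked. For those who decline, the gap stays open. Asking at the start still comes before a participant has been questioned about imminent risk, and it gives staff an answer to act on if the line drops later.

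Fifth, re-confirming the location takes time that the 0.5 to 2 minutes may not fully cover, since the risk questions could be triggered often in this population. That is fair, but the addition is small.

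**Conclusion.** The concern holds. In the supplied text, the home address is the only source named for reaching local emergency services, sessions are remote and not tied to the home, and no step records the current location. This is more than a missing detail, because following Section 3.9 as written could send help to the wrong place.

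No frequency can be given. The case for change rests on a possibly irreversible outcome set against an assumed 0.3% to 1.3% of session time. It assumes that no unseen consent text or staff procedure already records location. Because of that uncertainty and the existing safeguards, this is a change that should be made, held with medium confidence, and not a fatal defect. The aims, sample size and analysis do not change.

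**What to change.** - When contact details are collected or confirmed at the start of the session, as the last part of consenting, record the participant's current physical location and check that the telephone number on file is reachable.
- Confirm the location again on reconnection and whenever the three risk questions are asked.
- Amend Section 3.9 so that emergency services are contacted using the session location first. The home address is the back-up, including when a participant declines to give a location; the alternate contact also remains available.
- If a separate safety procedure already does this, refer to it in Section 3.9 instead.

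The clinical decisions in Section 3.9 stay as they are.

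The change needs one field and about two sentences in Section 3.9, possibly with a matching line in the consent section. Staff time is about 1 minute per session (assumed range 0.5 to 2), or 1.25 to 5 hours over 150 sessions, plus a little for re-confirmation. There are two other downsides. One more identifier is held, which can sit in the separate safety data set already due for deletion at study end. There may also be a small effect on disclosure in the attempt-history items that follow, which feed eligibility and stratification. The home address is already requested from everyone, and the question precedes randomization, so it is put to both arms alike.
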